8.3.2 UNANTICIPATED PROBLEM (UP) REPORTING

The investigator will report unanticipated problems (UPs) to the reviewing Institutional Review Board (IRB) and other study investigators. The UP report will include the following information:

- Protocol identifying information: protocol title and number, PI's name, and the IRB project number;
- A detailed description of the event, incident, experience, or outcome;
- An explanation of the basis for determining that the event, incident, experience, or outcome represents an UP;
- A description of any changes to the protocol or other corrective actions that have been taken or are proposed in response to the UP.

Unanticipated problems must be reported to participating investigators within **48 hours** of learning of the event, and to local IRBs per local IRB reporting policies.

Participating sites are responsible for ensuring compliance with local IRB policies and procedures on safety reporting, which may differ from those outlined in this protocol.

8.3.3 UNANTICIPATED ADVERSE DEVICE EFFECT (UADE) REPORTING

Unanticipated adverse device effects (UADEs) must be reported to participating investigators within **48 hours** of learning of the event, and to local IRBs per local IRB reporting policies.

Per 21 CFR 812.46, a sponsor shall immediately conduct an evaluation of any unanticipated device effects. A sponsor who determines that an unanticipated adverse device effect presents an unreasonable risk to subjects shall terminate all investigations or parts of investigations presenting that risk as soon as possible. Termination shall occur not later than 5 working days after the sponsor makes this determination and not later than 15 working days after the sponsor first received notice of the effect.

A sponsor who conducts an evaluation of an unanticipated adverse device effect under 812.46(b) shall report the results of such evaluation to FDA and to all reviewing IRB's and participating investigators

within 10 working days after the sponsor first receives notice of the effect. Thereafter the sponsor shall submit such additional reports concerning the effect as FDA requests 21 CFR 812.150(b)(1)).

Participating sites are responsible for ensuring compliance with local IRB policies and procedures on safety reporting, which may differ from those outlined in this protocol.

8.3.4 REPORTING UNANTICIPATED PROBLEMS (UPS) AND UNANTICIPATED ADVERSE DEVICE EFFECTS (UADES) TO PARTICIPANTS

Not applicable. Participation involves a one-time visit. Safety information will be reviewed as part of the initial consent process, and the consent will be obtained with new safety information as applicable.

9 STATISTICAL CONSIDERATIONS

9.1 STATISTICAL HYPOTHESES

No hypothesis tests will be performed. All statistical estimates (e.g., proportions, incidence rates, sensitivity, specificity, means, correlations, etc.) will be tabulated with 95% confidence intervals (CIs).

9.2 SAMPLE SIZE DETERMINATION

Cohort A will be imaged with OCT. Previous data on OCT demonstrate that established systems are sensitive with respect to detecting Barrett's mucosa. For instance, Poneros et al (2001) found a 97% sensitivity rate using OCT in 38 patients²⁹. At this stage of development, if we can achieve at least 70% sensitivity, then the device will pass initial testing. If optimal sensitivity is 95%, and the lowest acceptable sensitivity is 70%, then we will require at least 14 patients with evaluable data in each group (42 total in Cohort A) to assess whether the device adequately meets this threshold with 85% power.

Cohort B will be imaged with a/LCI. Our group previously conducted and published a study in 2011 using single-point a/LCI to measure nuclear diameter as an indicator of dysplasia in the esophagus.¹³ The primary differentiating characteristic between dysplastic and normal tissue was nuclear diameter (measured by a/LCI). For dysplastic tissue, the mean nuclear diameter and standard deviation was $13.0 \pm 1.1 \mu\text{m}$, and for normal tissue, the same respective values were $10.3 \pm 1.7 \mu\text{m}$. This difference was highly statistically significant, and we rejected the null hypothesis (no difference between normal and dysplastic nuclear diameters) with a p-value of 0.0001.

To determine the number of targeted patient enrollments in Cohort B, we conducted a statistical power analysis based on our previous results. For a sample size of 20 patients with dysplasia and 20 patients with normal esophageal tissue, and targeting the same p-value of 0.0001, we expect a robust statistical power of 97% when conducting a two-sample t-test for nuclear diameter distributions matching our observations from the 2011 study. We would therefore expect a 97% chance of validating our previous observations at the same level of significance for a sample size of 20. Comparatively, for a sample size

of 10 patients in each category, our power would be only 36%, far too low; for a sample size of 30 patients in each category, our power would be greater than 99.9%, which is unnecessarily high. Therefore, for Cohort B, we will target 20 patients with dysplasia and 20 normal patients to achieve a strong statistical power without an undue excess in patient enrollment.

To accommodate Cohort B, which will be receiving the dual modality a/LCI-OCT probe, we have therefore changed the sample size to be a total of 82 (42 in Cohort A, and 40 in Cohort B).

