5 STUDY POPULATION

5.1 INCLUSION CRITERIA

Subjects must meet all of the following criteria to be eligible for this study:

1. Presenting to UNC for routine care upper endoscopy
2. Meet one of the following criteria:
 - 2.1. Cohort A
 - 2.1.1. Presenting to UNC for upper endoscopy of GI conditions without esophageal symptomatology with no history of gastroesophageal reflux disease (GERD) or other esophageal condition affecting the epithelium (asymptomatic controls). Esophageal

symptomology includes, but is not limited to, heartburn, globus, chest pain, dysphagia, and odonophagia OR,

- 2.1.2. Current dysplastic or non-dysplastic Barrett's Esophagus of any length OR,
- 2.1.3. History of dysplastic or non-dysplastic Barrett's Esophagus after treatment with endoscopic eradication therapy (EET)

OR

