8.1.2.1 PROBE ADMINISTRATION, ESOPHAGEAL IMAGES, AND RESEARCH BIOPSIES

Subjects will proceed with routine care EGD, during which esophageal landmarks will be identified, and the OCT or a/LCI-OCT device administered. In brief, the probe will be affixed to the end of the endoscopy using a plastic band, in a manner similar to that used to deliver other devices into the esophagus. The device and endoscope tip will be passed through the posterior pharynx and the upper esophageal sphincter under direct endoscopic visualization. Areas of normal squamous epithelium can be easily identified endoscopically, as can areas of columnar mucosa in the esophagus, based on the endoscopic appearance. The OCT or a/LCI-OCT combined device will be apposed to both normal and columnar (Barrett's) tissue, by deflection of the endoscope tip. Images will be acquired by the device, as detailed below, and subjects enrolled in cohort B will also receive research-specific biopsies as detailed below. The indentation on the tip of the probe will create a transient tissue bump that is visible endoscopically to allow for concurrent research biopsies after images are taken. After acquisition of these images and research biopsies (as applicable), the remainder of the study will be performed as per the standard of care.

Erosions, erosive disease, and areas of inflammation will be avoided when placing the paddle for probe administration. Adequacy of device-to-epithelium contact will be measured based on the quality of the OCT image. In images with poor contact, esophageal mucosal layers are poorly defined. In this situation, the probe will be repositioned in an effort to improve image quality. A good image is that in which esophageal mucosal layers are clearly defined in the OCT image.

COHORT A:

During the procedure, the OCT device will be administered, and at least one white light image and at least one narrow band image will be taken from the following locations of the esophagus:

- 1) 3 centimeters above the top of the gastric folds (TGF-3)
- 2) 5 centimeters above the top of the gastric folds (TGF-5)
- 3) Any planned clinical biopsy locations

COHORT B:

During the procedure, the a/LCI-OCT device will be administered, and at least one white light image and at least one narrow band image will be taken from the following locations of the esophagus:

- 1) 3 centimeters above the top of the gastric folds (TGF-3)
- 2) 5 centimeters above the top of the gastric folds (TGF-5)

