9.4 STATISTICAL ANALYSES

This is a pilot study collecting data for OCT and a/LCI-OCT device optimization. This study will provide initial images for the investigational device, and depending on the device's accuracy in discerning tissue, these data will help form the basis for further investigations. Data analysis will consist of simple bivariate analysis, with endoscopy results being compared to a/LCI-OCT image results. Specifically, 2 x 2 tables of OCT, a/LCI-OCT, and endoscopy results will be constructed, with each imaging site being categorized as columnar versus squamous. Sensitivity will be defined as the proportion of sites correctly categorized by OCT, or a/LCI-OCT, using endoscopy results as the gold standard. Measures of variability of sensitivity results will be generated using non-parametric statistics.

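### Sections 9.1, 9.2 and 9.4 do not describe the same decision: the 85% power belongs to an unstated 13-of-14 rule, sensitivity is defined as overall accuracy by site, and the t-test that sized Cohort B is excluded and unplanned

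*Combined protocol and SAP*

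**What the plan says.** **Pass rule and power (9.2, Cohort A).** The criterion is "if we can achieve at least 70% sensitivity, then the device will pass initial testing". The section sets 95% as the optimal sensitivity and 70% as the lowest acceptable, and asks for 14 patients with evaluable data in each of three groups "to assess whether the device adequately meets this threshold with 85% power". It gives no alpha, sidedness, test or passing count.

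**Inference (9.1).** "No hypothesis tests will be performed". Estimates, with sensitivity, specificity and means among the examples, are to carry 95% confidence intervals.

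**Analysis (9.4).** Tables are built "with each imaging site being categorized as columnar versus squamous". Then: "Sensitivity will be defined as the proportion of sites correctly categorized by OCT, or a/LCI-OCT, using endoscopy results as the gold standard". On uncertainty: "Measures of variability of sensitivity results will be generated using non-parametric statistics".

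**Tissue imaged (8.1.2.1).** The probe "will be apposed to both normal and columnar (Barrett's) tissue".

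**Cohort B (9.2).** The 20 + 20 patients are justified by a two-sample t-test comparing nuclear diameter in dysplastic and normal tissue at a p-value of 0.0001, with 97% power. Section 9.4 contains no nuclear-diameter analysis and no dysplastic-versus-normal comparison.

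**The concern.** A power figure belongs to one decision rule. Here the rule a reader can find (reach 70%), the inference in 9.1 (95% intervals, no tests) and the printed power lead to three different passing counts. An observed 10, 11 or 12 of 14 meets the written threshold but fails the rule that has 85% power, so the team could not say from the plan whether the device had passed. This matters because 9.2 makes it a pass/fail step and 10.1.2 lets interim accuracy results prompt early termination.

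Section 9.4 adds a second difficulty. Section 9.2 counts patients and concerns detection of Barrett's mucosa. Section 9.4 counts sites and, as worded, credits correct calls on squamous tissue to sensitivity. Easy squamous sites could then lift a poor detector over 70%.

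In Cohort B, the comparison that fixed enrolment of 40 of the 82 patients has no place in the analysis plan.

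**Working it through.** **1. Reproducing the 85%.** Inputs from 9.2: n = 14, floor p0 = 0.70, target p1 = 0.95. Alpha is not stated, so one-sided 5% is assumed. With X the number of Barrett's patients correctly identified, X ~ Binomial(14, p).

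- Power of X ≥ 13 at 0.95: 14 × 0.95^13 × 0.05 + 0.95^14 = 0.359 + 0.488 = **0.847**.
- Alpha at 0.70: 14 × 0.70^13 × 0.30 + 0.70^14 = 0.0407 + 0.0068 = **0.0475**.

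This matches the printed 85%. The neighbouring cut-offs do not:

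| Passing count | Pass if true 70% | Pass if true 95% |
|---|---|---|
| ≥ 10/14 (observed ≥ 70%) | 58.4% | 99.96% |
| ≥ 12/14 | 16.1% | 97.0% |
| ≥ 13/14 | 4.75% | 84.7% |
| 14/14 | 0.68% | 48.8% |

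**2. The written threshold.** 0.70 × 14 = 9.8, so an observed 70% means 10/14. The first row of the table applies.

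**3. The interval in 9.1.** The exact (Clopper-Pearson) 95% interval at 13/14 is 66.1% to 99.8%, which includes 70%. Only 14/14 excludes it, and the last row gives power 48.8%.

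**4. Which patients count.** One of the three Cohort A groups is normal controls (1.1), in whom sensitivity for Barrett's mucosa cannot be estimated. Two Barrett's groups of 14 remain, and neither is named as deciding. If they are pooled, n = 28 and X ≥ 24 gives alpha 4.7% and power 98.8%. Section 5.1 also admits patients with only a treated history of Barrett's, who need not have columnar tissue to image.

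**5. Sensitivity as worded in 9.4.** Assumptions, not document figures: one columnar and one squamous site per Barrett's patient, 14 patients, sites independent. There are 28 sites, and 70% of 28 = 19.6, so 20 correct calls pass.

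- If all 14 squamous sites are right, 6 of 14 columnar sites are enough. P(Binomial(14, 0.50) ≥ 6) = **0.788**.
- If squamous sites are right 95% of the time, the same device passes in 66% of trials.
- At 40% columnar detection the expected score is (14 + 14 × 0.40)/28 = 0.70. It passes in 51% of trials with all squamous sites right, and in 38% with 95% right.

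**6. Cohort B, three sections compared.** Section 9.2 sizes on a t-test of nuclear diameter. Section 9.1 excludes tests. Section 9.4 tabulates only columnar versus squamous. The general reference to means in 9.1 could cover group summaries but does not specify the between-group comparison.

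The same design stated as precision, using the values in 9.2 (13.0 ± 1.1 and 10.3 ± 1.7 µm, 20 per group):

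- Difference = 13.0 − 10.3 = 2.7 µm.
- SE = √((1.1² + 1.7²)/20) = √(4.10/20) = 0.453 µm.
- Welch df = 32.5, t = 2.036, so the 95% half-width = 2.036 × 0.453 = **0.92 µm**.

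**The case against.** The strongest reply is that 9.2 uses ordinary null-and-alternative language: a lowest acceptable value, an optimal value, and power to assess the threshold. Read that way, 85% is right. This stands, and a reader who inferred a miscalculation would be wrong. The reply does not supply the missing alpha and cut-off, and 9.1 excludes the test it needs.

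On 9.4, 9.1 lists sensitivity and specificity separately, 9.2 speaks of detecting Barrett's mucosa, and a 2 × 2 table yields both measures. The usual definitions were probably intended. That makes the sentence a drafting fault, but it is the operative definition and should be corrected.

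Three stronger inferences are not supported:

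- **Columnar sites are confined to 3 and 5 cm above the gastric folds.** Section 8.1.2.1 adds planned clinical biopsy locations and allows the imaging locations and number to vary. Cohort A's entry criterion "Current dysplastic or non-dysplastic Barrett's Esophagus of any length" therefore does not by itself leave short segments unimaged. The open question is treated patients with no remaining columnar tissue.
- **Losing one patient would wreck the power.** At n = 13, 12/13 has alpha 6.4% and power 86.5%. Any sharp drop under a strict 5% limit is largely the coarseness of small binomial counts.
- **The 97% for Cohort B is wrong.** Section 9.2 states neither sidedness nor variance assumption, and its means and SDs are rounded, so no error can be established.

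Finally, this is a pilot whose synopsis lists no endpoints, and a point-estimate screen is a legitimate choice. If that is the choice, 85% is not its power.

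**Conclusion.** The concern holds as an internal inconsistency among 9.1, 9.2 and 9.4.

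- **Cohort A:** the printed 85% is the power of an unstated 13/14 rule at one-sided 5%. It describes neither the observed-70% rule nor exclusion of 70% by the exact 95% interval. These figures assume one independent result per Barrett's patient.
- **Definition of sensitivity:** as worded, 9.4 measures overall accuracy by site. The 79% pass rate for a device detecting half of columnar sites rests on the assumed site mix and perfect squamous calls. It illustrates the wording and does not forecast the trial.
- **Cohort B:** this is a direct conflict in the text and needs no assumption.

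Nothing here shows that 82 patients is too few.

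**What to change.** 1. **9.2, Cohort A: choose one.**
   - (a) State the powered rule: pass if Barrett's mucosa is correctly identified in at least 13 of 14 Barrett's patients with columnar tissue imaged (one-sided alpha 4.75%, power 84.7% at 95%). Name the deciding group, or pool both and print, for example, at least 24 of 28 (alpha 4.7%, power 98.8%). Say how a patient with several columnar sites is scored and how the cut-off is reset if fewer patients contribute. List the rule in 9.1 as an exception, and note that the 95% interval at 13/14 (66.1% to 99.8%) still includes 70%.
   - (b) Keep the observed-70% screen, delete the 85% power, and print its per-patient pass rates: 58.4% at a true 70% and 99.96% at a true 95%.
2. **9.4, definitions.** Define sensitivity as columnar sites called columnar and specificity as squamous sites called squamous. Name a 95% interval that allows for several sites per patient, such as a bootstrap that resamples patients.
3. **Cohort B.** Add the dysplastic-versus-normal nuclear-diameter comparison (mean difference with 95% interval) to 9.4. Then either list the t-test as an exception in 9.1, with sidedness and variance assumption stated, or restate 9.2 as precision: about ±0.92 µm around a 2.7 µm difference with 20 per group.

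**Cost.** Wording only; the target of 82 is unchanged. Option (a) commits the team to a stricter explicit rule and counts only patients with columnar tissue imaged. Option (b) gives up the 85% claim.

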
9.3 POPULATIONS FOR ANALYSES

All subjects who were administered the probe, regardless of enrolling cohort, will have data included for optimization unless withdrawn per section 7.2. For this study, an enrolled subject is defined as a subject who was successfully administered the device and for whom we have evaluable data.

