6 STUDY INTERVENTION

6.1 DEVICE DESCRIPTION

The purpose of this instrument is to obtain optical measurements from the esophageal mucosa via an endoscopic probe. The imaging modalities used by this probe are angle-resolved Low-Coherence Interferometry (a/LCI), a technology that measures the depth- and angle-dependent scattering of light by tissue and Optical Coherence Tomography (OCT), a depth-resolved optical imaging technology. These optical readings provide indications of subsurface tissue architecture and will assist in the detection and diagnosis of metaplastic and dysplastic conditions such as Barrett's esophagus.

The probe is designed to be used in conjunction with the visual guidance provided by a commercial endoscope. The probe has mechanical features similar to a radiofrequency ablation (RFA) "paddle",

which is externally attached to an endoscope to provide ablative therapy under visual guidance of the endoscope. This form is advantageous because it is known to be well-tolerated and easily passed when mounted on the endoscope. It will also eventually allow the development of a single paddle that could both image and treat diseased mucosa.

Once inserted into a patient's esophagus and placed against the tissue surface, the probe will acquire 2D OCT images of the tissue surface at operator-selected locations. Some of the optical data received will be displayed in real-time. All optical data will also be stored on a computer for post hoc analysis.

The components of the combined probe system a/LCI-OCT instrument are grouped into the following modules: 1) Optical probe, 2) OCT engine, 3) a/LCI engine, 4) computer system, and 5) physical enclosure.

6.1.1 aCI/OCT OPTICAL PROBE

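### The same subjects feed device optimisation and the accuracy estimate, with no reading rule fixed beforehand, so the OCT sensitivity set against the 70% bar may be optimistic

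*Combined protocol and SAP*

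**What the plan says.** Section 9.3 gives the only analysis population: "All subjects who were administered the probe, regardless of enrolling cohort, will have data included for optimization unless withdrawn per section 7.2". Section 7.2 adds that data from withdrawn subjects are not used.

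Section 9.4 describes the study as data collection for device optimisation. It then takes sensitivity from 2 x 2 tables in which each imaging site is called columnar or squamous, with endoscopy as the reference. It adds that "depending on the device's accuracy in discerning tissue, these data will help form the basis for further investigations". Section 6.1 says: "All optical data will also be stored on a computer for post hoc analysis".

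Two decisions hang on the resulting accuracy:

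- Section 9.2 says of OCT that "if we can achieve at least 70% sensitivity, then the device will pass initial testing", and sizes Cohort A at 14 evaluable patients per group "to assess whether the device adequately meets this threshold with 85% power".
- Section 10.1.2 plans interim assessments of device performance that could lead to early termination if accuracy proves inadequate or very high.

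Section 9.1 says "No hypothesis tests will be performed" and promises 95% confidence intervals for all estimates.

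The plan gives no rule for calling an image columnar or squamous, no date for locking one, no reading blinded to endoscopy, no training/test split and no cross-validation. The one image criterion, in section 8.1.2.1, concerns contact quality (whether mucosal layers are clearly defined), not tissue type.

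**The concern.** A sensitivity estimate and its interval mean what they say only if the rule being scored was settled without sight of the data that score it. Here the device is newly developed, no reading rule is stated, and every usable image is available for optimisation. Nothing in the plan stops the columnar/squamous rule from being shaped on the images it is then graded on. In that case the reported sensitivity tends to be too high, and the interval treats a chosen rule as a given one.

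The practical risk is a device with true sensitivity near or just under 70% that passes initial testing, or that looks strong at an interim assessment, partly because its rule was fitted to those patients.

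**Working it through.** **Inputs.** From section 9.2: lowest acceptable sensitivity 0.70, optimal sensitivity 0.95, 14 patients per group, power 85%; nuclear diameters 13.0 ± 1.1 µm (dysplastic) and 10.3 ± 1.7 µm (normal), 20 per group. Assumed: one site per patient; one-sided alpha of 0.05 (the plan states none); normal distributions; the number of candidate rules, K, and the correlation between them.

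**1. The plan's own figure.** With X ~ Binomial(14, p), require X ≥ 13.
- P(X ≥ 13 | p = 0.70) = 0.0475
- P(X ≥ 13 | p = 0.95) = 0.847

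This matches the stated 85%. The calculation treats the rule as fixed in advance.

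**2. Locked rule, point-estimate reading of the bar.** Since 9/14 = 64.3% and 10/14 = 71.4%, an observed sensitivity of at least 70% means X ≥ 10. At a true sensitivity of 0.65, P(X ≥ 10) = 0.423.

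**3. Best of K rules, chosen and scored on the same 14 patients.** If the rules are independent and equally good, P(best passes) = 1 − (1 − P)^K.

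| Case | Locked | K = 3 | K = 5 |
|---|---|---|---|
| True 65%, bar 10/14, independent rules | 42% | 1 − 0.577³ = 81% | 1 − 0.577⁵ = 94% |
| True 65%, bar 10/14, latent correlation 0.8 (simulated) | 42% | 64% | 73% |
| True 70%, bar 13/14, independent rules | 4.75% | 1 − 0.9525³ = 13.6% | 1 − 0.9525⁵ = 21.6% |

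At a true 65%, mean apparent sensitivity is 72–76% for K = 3 and 74–79% for K = 5. The lower ends belong to the correlated rules.

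If both Barrett's groups of Cohort A are pooled (28 patients, bar 20/28), the chance of passing at a true 65% is 31% with a locked rule. For K = 3 it is 67% with independent rules (1 − 0.691³) and 52% with correlation 0.8.

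**4. One tuned cut-off.** In simulation, the cut-off maximising sensitivity + specificity was chosen on the data and scored on the same data.

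| Setting | Apparent sens/spec | True sens/spec | Gap |
|---|---|---|---|
| Weak separation (best attainable 65%/65%), 14 per group | 72%/72% | 63%/63% | about 9 points |
| Diameter distributions of section 9.2, 20 per group | 91.5%/83.4% | 86.5%/78.3% | about 5 points |

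The second row only shows the scale for a well-separated measurement. Section 9.4 plans no diameter cut-off, and the true values in that row already exceed 70%.

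**The case against.** The strongest reply is that the documents speak of optimising the device. That may mean hardware or signal processing for a later version. They never say that a reading rule will be tuned on these images and then re-scored on them. This stands. A reader might infer that the reported accuracy is bound to be overstated; the text supports only that it may be, depending on how the rule is formed.

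Two further inferences are tempting and also fail:

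- **That specificity faces the 70% bar.** The bar sits in the Cohort A paragraph and concerns OCT sensitivity. Specificity is named in section 9.1 without a target.
- **That an untuned nuclear-diameter cut-off or tissue depth is missing.** Diameter enters section 9 only through the sizing of Cohort B, as a t-test on means, which needs no cut-off. Section 9.4 classifies columnar versus squamous, not dysplasia. It does put a/LCI-OCT results in a 2 x 2 table, so some rule for that call is still needed.

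It can also be said that this is a pilot whose images do not guide care (section 2.3.2) and do not categorise participants (section 8.1.2.1). That limits the harm and protects the reference standard. It does not protect the device reading, and the protocol itself attaches a pass criterion and possible early termination to the result.

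**Conclusion.** The point holds in conditional form. The plan uses the same subjects for optimisation and for the accuracy estimate, and contains nothing that separates forming the rule from scoring it. If the rule is developed on these images, OCT sensitivity may be optimistic and its interval does not account for that.

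A plausible size is 5 to 9 points for one tuned cut-off at 14 to 20 per group. With 14 patients and a true sensitivity of 65%, the chance of reaching 10/14 rises from 42% to at most 81% with three candidate rules, and to about 64% if they are strongly correlated. These figures rest on an assumed number of rules, normal distributions and one site per patient; none of these is given in the plan. The optimism matters for a device near 70%. For one well above it, such as the 95% taken as optimal, the pass decision would hardly change.

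**What to change.** In sections 9.3 and 9.4:

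1. Write down the columnar/squamous rule for OCT and for a/LCI-OCT before images are scored against endoscopy, and have images read without knowledge of the endoscopy result.
2. If any part of the rule is tuned on study data, report leave-one-patient-out cross-validated sensitivity and specificity, with the whole tuning step repeated in each fold. Leave out patients, not sites. Base the 70% decision and the interim assessments on that estimate. This needs a tuning step that can be rerun; criteria settled by eye must be fixed under item 1.
3. Label any accuracy computed on the tuning data as apparent.
4. Optionally, apply the Cohort A OCT rule unchanged to the Cohort B OCT images as a supportive external check. The probe and case mix differ, so a drop could not be attributed to tuning alone, and this should not replace the Cohort A estimate.

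Splitting Cohort A is not a workable alternative. With 7 patients per group held out, even 7/7 gives alpha 0.70⁷ = 0.082 and power 0.95⁷ = 0.698.

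The cost is SAP wording, minor programming and some reading logistics. No patients or procedures are added, and all data remain available for optimisation afterwards. The reported accuracy may come out a few points less favourable.
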